
PURPOSE

We propose to conduct the first randomized controlled trial to test whether a cessation intervention in the PED setting can reduce caregiver smoking and decrease children's SHSe.

Primary Aim 1: To evaluate the efficacy of the SBIRT compared to Healthy Habits Control (HHC) condition. Primary outcomes are self-reported prolonged abstinence and point prevalence at 6-weeks and 6-months post-enrollment, validated in all participants via expired carbon monoxide and salivary cotinine. Secondary outcomes include number of cigarettes smoked, quit attempts, readiness to quit, and use of cessation resources.

Hypothesis 1: Caregivers who receive the SBIRT will have higher prolonged abstinence and point prevalence cessation rates compared to caregivers in the HHC condition.

Primary Aim 2: To evaluate the efficacy of the SBIRT on reducing children's SHSe. Outcomes are caregiver reports of total home/car smoking bans and reductions in SHSe (validated using salivary cotinine in children).

Hypothesis 2: Children of SBIRT caregivers will have higher total home/car smoking bans and lower home/car smoking exposure compared to children of HHC caregivers.

Primary Aim 3: To explore mediators and moderators of the SBIRT outcomes.

Hypothesis 3: The SBIRT intervention effect on prolonged abstinence and point prevalence cessation rates will be mediated by the caregiver's perception of the risk of smoking on their child's health and the caregiver's motivation to quit over time. The intervention effect will be moderated and attenuated by factors such as household smokers, financial strain, and low social support to quit.

Secondary Aim 1: To conduct a cost analysis to determine the numbers of SHSe-related PED visits and hospitalizations in children of caregivers in the SBIRT condition compared to children of caregivers in the HHC condition. This will provide a basis for a future, full-scale cost-benefit analysis.

Secondary Aim 2: Using the findings from this project and our prior research, we will develop a manual of operations and a comprehensive package of provider and patient materials that will be disseminated for use in other PEDs and EDs nationwide.

Secondary Aim 3: To quantify the prevalence and identify correlates of Cannabis Smoke Exposure and SHSe among SHS-exposed PED patients.

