Primary Aim 3, Hypothesis 3: We hypothesize that the SBIRT intervention effect on prolonged abstinence and point prevalence cessation rates will be mediated by the caregiver's perception of the risk of smoking on their child's health, or on their readiness to quit over time.^{42,66,67,69,70,99} Bivariate analyses will be used to initially examine if the variables measuring this phenomena, susceptibility, severity and benefits of quitting are associated with cessation at each time point and if there are any changes in perceived health risk from baseline to 6-months in the SBIRT versus HHC groups. We will build on the models from our primary aim to determine the association of these potential mediators. Analysis assessing these effects will be conducted using abstinence at each follow-up point as the dependent variable and testing for interactions between treatment (i.e., intervention) and the potential mediator. Additionally, we will examine the main effects of the intervention within each level of the mediator to establish whether the intervention is effective in each subgroup, acknowledging that we may be underpowered for some subgroups.

Mediation analysis: To assess whether our intervention improved cessation outcomes via the proposed mediators, we will perform mediation analyses using both the criteria of Baron & Kenny¹⁰⁰ and Holmbeck.¹⁰¹ As our outcome variables are dichotomous, we will apply the method of Huang et al.,¹⁰² which involves a system of logistic regression models and the Monte Carlo method to assess posterior distributions of the direct, indirect, and relative indirect effects. Three sets of logistic regression analyses will be performed, as the variables of interest; outcome, intervention and mediator are mainly categorical. The first 2 steps are to assess the intervention effects on the outcome and the mediator. In the third step, we will assess the relationship between each of the proposed mediators and the study outcome at each follow-up. The same 3 steps will be repeated with adjustment for potential confounders and/or moderators as determined from analysis for Hypothesis 3. The mediating variables that will be considered are: perception of child's risk from SHSe and the benefits to the child of quitting, also motivation to quit, self-efficacy. Moderating variables are household smokers, financial strain, , nicotine dependence, and prior quit attempts.

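### The Aim 3 section assesses mediators by treatment-by-mediator interactions and within-level effects, which address moderation; the formal mediation method that follows leaves mediator timing and arm adjustment unstated

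*Combined protocol and SAP*

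**What the plan says.** The aim is labelled primary but worded as exploratory: "Primary Aim 3: To explore mediators and moderators of the SBIRT outcomes".

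In the Analytic Plan, the first paragraph under Primary Aim 3, Hypothesis 3 takes abstinence at each follow-up as the dependent variable and assesses the mediator effects by "testing for interactions between treatment (i.e., intervention) and the potential mediator". It adds that "we will examine the main effects of the intervention within each level of the mediator", so as to judge whether the intervention works in each subgroup, and concedes that power may be low.

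The next paragraph, headed Mediation analysis, is separate. There "we will perform mediation analyses using both the criteria of Baron & Kenny" and Holmbeck, together with a system of logistic regressions and "the Monte Carlo method to assess posterior distributions of the direct, indirect, and relative indirect effects". It has three steps. "The first 2 steps are to assess the intervention effects on the outcome and the mediator"; the third relates each mediator to the outcome at each follow-up. The steps are then repeated with adjustment for confounders and/or moderators taken from the Hypothesis 3 analyses. A structural equation model of the whole theory follows.

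The mediator list ends with "also motivation to quit, self-efficacy". Hypothesis 3 in the Purpose section names as moderators "factors such as household smokers, financial strain, and low social support to quit"; the moderator list in the Mediation analysis paragraph does not include social support.

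**The concern.** A treatment-by-mediator interaction asks whether the intervention effect differs across values of the mediator. Mediation asks whether the intervention moves the mediator and the mediator in turn moves the outcome. An effect can be wholly mediated with no interaction, and an interaction can exist with no mediation.

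The within-level comparison has a further problem if the levels are post-baseline. Caregivers with high risk perception at 6 weeks under SBIRT and under HHC are no longer randomised groups: the intervention has helped decide who is in each, so any shared cause of risk perception and quitting can bias the contrast. Calling such levels subgroups invites an efficacy reading that they cannot carry.

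The formal method is the right kind of analysis, but two details that decide its interpretation are missing: when the mediator is measured relative to the outcome, and whether the mediator-outcome step is adjusted for arm. The plan also does not say which of its several analyses governs the answer to Hypothesis 3.

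**Working it through.** The plan gives no sample size or power figure for mediation, so there is none to reproduce. The check has three parts.

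**1. What the two tests respond to**

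Inputs from Sample Size and Power Estimates: 6-month point prevalence 6.3% (HHC) and 12% (SBIRT); 300 per arm, or 375 under the multiple imputation assumption. Assumptions of mine: a binary mediator, its prevalence in each arm, no mediator-outcome confounding, and Wald tests at two-sided 0.05 (the power section states no alpha). There were 20,000 simulated trials per scenario.

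For arm x and mediator level m, with Y quitters among N caregivers, L(x,m) = ln[(Y + 0.5)/(N − Y + 0.5)], with variance 1/(Y + 0.5) + 1/(N − Y + 0.5).

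- Interaction: L(1,1) − L(0,1) − L(1,0) + L(0,0).
- Effect within level m: L(1,m) − L(0,m).
- Indirect effect: significant only if both the arm-to-mediator log odds ratio and the mediator-to-outcome log odds ratio (pooled within arm) have |z| > 1.96. This stands in for the planned Monte Carlo method.

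Full mediation means that the quit rate depends on the mediator alone. With mediator prevalence p0 in HHC and p1 in SBIRT, the difference in quit rate between mediator levels is d = (0.12 − 0.063)/(p1 − p0), and the rate at the low level is 0.063 − p0·d.

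| p0, p1 | d | Quit rate, low / high mediator |
|---|---|---|
| 20%, 70% | 0.114 | 4.0% / 15.4% |
| 30%, 70% | 0.1425 | 2.0% / 16.3% |
| 30%, 60% | 0.190 | 0.6% / 19.6% |

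For no mediation, the mediator is at 50% in both arms and the effect is confined to one level: 6.3% in HHC against 17.7% in SBIRT at that level, and 6.3% in both arms at the other. SBIRT overall is then 0.5 × 6.3% + 0.5 × 17.7% = 12%.

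| Share of trials significant | Full mediation (range over rows and both n) | No mediation, n = 300 / 375 per arm |
|---|---|---|
| Interaction | 0.2–3.7% | 45% / 55% |
| Within level (in the level with the effect, for the last column) | 0.04–4.7% | 86% / 93% |
| Indirect effect | 98–100% | 3% / 4% |

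The low rates under full mediation are correct behaviour: there is no interaction and no residual within-level effect to find. They fall below 5% because cells are sparse. In the first row at 300 per arm, expected quitters are 300 × 0.80 × 0.0402 = 9.6 and 300 × 0.20 × 0.1542 = 9.3 in HHC, and 300 × 0.30 × 0.0402 = 3.6 and 300 × 0.70 × 0.1542 = 32.4 in SBIRT.

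**2. Timing**

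Table 1 schedules risk perception, benefits of quitting and motivation at baseline (T0), 6 weeks (T1) and 6 months (T2). For abstinence at T1, the only post-baseline mediator value comes from the same visit. The point-prevalence question looks back over 7 days, so the outcome period precedes the mediator answer, and quitting may have changed the belief rather than the reverse. For abstinence at T2, a T1 mediator is available, but the plan does not say that it will be used.

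**3. Measures**

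Neither self-efficacy nor social support to quit appears in Table 1 or in the numbered measures, which run from item 3 to item 6. Confidence to quit and social support appear under the SBIRT Advise step only as counselling content, not as a measure taken in both arms.

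**The case against.** The strongest reply is that the plan already contains the right analysis. The question whether the intervention works through the mediators is assigned to the formal paragraph, and its two core mediators, risk perception and motivation, are measured three times. That stands. A reader might infer that mediation rests on the two moderation-type tests, that Hypothesis 3 cannot be tested, or that mediation would almost always be missed. The documents do not support this: the low detection rate belongs to the interaction test alone, and no text says that a null interaction will be read as no mediation.

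Three further points stand in part.

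- The follow-up wording in step 3 may date only the outcome, and mediator levels could mean baseline levels. It is therefore not established that the mediator is always concurrent or post-randomisation, only that the plan does not say.
- A treatment-by-mediator interaction has a legitimate use as a check when separating direct from indirect effects, so it need not be deleted outright.
- A reader might infer that self-efficacy and social support are unmeasured. The questionnaires (Appendices A, G and H) are listed but not supplied, and the numbering gap may reflect edited or lost text. Only the absence of a described measure can be asserted.

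What the reply does not remove is that the first paragraph offers moderation analyses as assessments of mediators, and that the formal models may take their adjustment set from those same Hypothesis 3 analyses.

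**Conclusion.** The point holds as one of specification and labelling within an exploratory aim; it is not a missing mediation analysis. Followed as written, the first paragraph can mislead in both directions: no signal when the effect is fully mediated, and a frequent signal (45 to 55% for the interaction) when there is no mediation.

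Those figures depend on the assumed mediator prevalences and on no confounding. The 98 to 100% must not be read as the trial's power for mediation: the assumed shifts in the mediator are large (30 to 50 percentage points), and prolonged abstinence would yield only about 300 × 0.021 + 300 × 0.07 = 27 quitters, against 300 × 0.063 + 300 × 0.12 = 55 for point prevalence. I put no figure on the bias in within-level comparisons, because it depends on unmeasured common causes about which the documents give nothing.

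Self-efficacy and social support are a minor consistency matter. The efficacy analyses for Aims 1 and 2 are unaffected.

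**What to change.** Change the Analytic Plan text for Primary Aim 3 as follows.

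1. Restrict interaction and subgroup-effect analyses to baseline moderators. Drop the within-level efficacy analysis for post-baseline mediators.
2. Keep any treatment-by-mediator interaction only as a check inside the formal mediation model, not as evidence for or against mediation.
3. Make the planned logistic indirect-effect method the lead mediation analysis, with the mediator at T1 and abstinence at T2, adjusted for arm, the baseline mediator and baseline confounders named in advance.
4. State two limits: caregivers who quit before T1 still leave direction uncertain, and unmeasured mediator-outcome confounding remains.
5. Reconcile self-efficacy and social support across the Purpose section, the measures, the Mediation analysis paragraph and the questionnaires, naming the instrument for each or removing the variable.

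The cost is wording only, since the T0, T1 and T2 measurements of the core mediators are already scheduled. The small downside is that 6-week abstinence no longer has a lead mediation analysis.

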
Given our prior experience⁵⁴ and proposed techniques, we conservatively project an 80% retention rate at 6 months.

Outcome Measures. Primary outcomes will be caregiver prolonged abstinence and 7-day point prevalence of tobacco use at 6-weeks and 6-months. Secondary caregiver outcomes will include cigarettes smoked, quit attempts, readiness to quit, and use of NRT and cessation resources (QL, smokefreeTXT, smokefree.gov). Child outcomes will be presence or absence of total home/car smoking bans, reported SHSe, and number of SHSe-related PED visits and hospitalizations at CCHMC.

Baseline Assessment. (Table 1) The brief baseline assessment (T0) will be conducted using a self-administered electronic survey to be completed on a tablet computer. The assessment items chosen are empirically validated measures from studies conducted with low-income disadvantaged study populations.^{42,66-71,39,63-68} The items are brief, easily comprehensible, and take into account low literacy levels. They are as follows:

Table 1: Measures for Baseline and Follow-up Assessments by Assessment Point	T0	T1	T2
Demographics; Financial Strain, , Household Smokers,	✓		
Tobacco Use History, Nicotine dependence, , Motivation to Quit	✓	✓	✓
Risk Perceptions: Child; Benefits of Quitting: Child	✓	✓	✓
Child's SHSe, , Child SHSe - related PED visits or Hospitalizations	✓	✓	✓
Healthy Habits Lifestyle- daily: fruits/vegetables, screen time, exercise, sugary drinks	✓	✓	✓
SBIRT and HHC Satisfaction,	✓		
Prolonged abstinence, point prevalence, nicotine dependence, readiness to change, quit attempts		✓	✓
Cessation Resource utilization: NRT, QL, SmokefreeTXT, Smokefree.gov, or other resources	✓	✓	

1. Demographics and tobacco use. We will collect gender, age, race/ethnicity, level of education, employment status, , number of cigarettes smoked daily, time to the first cigarette of the day, nicotine dependence, number of attempts to quit >24 hours, use of pharmacological and/or behavioral treatments for quitting, motivation to quit using the Contemplation Ladder, and stage of change in readiness to quit.^{41,72} Questions will also be asked about marijuana use by the participant and household members; participants will not be required to answer these questions. Participants who consented prior to Version 11 of the protocol may be re-consented at follow-up such that we may obtain information about marijuana use.

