2. Financial Strain. Three items will be used to measure financial strain.⁷⁴ The questions are: "How difficult is it for you to live on your total household income right now?", "In the next three months, how often do you think that you or your family will experience a bad time such as poor housing or not having enough food?", and "In the next three months, how often do you expect that you will have to do without the basic things that your family needs?" The three items will be measured on five-point scales and averaged to create a financial strain score ($\alpha = .802$). Higher scores will reflect more financial strain.

3. Risk perception to child. Perceived vulnerability regarding the effects of his/her smoking on their child will be assessed using adapted measures by Borelli et al. Perceived Vulnerability-Child will be measured with items including: "How concerned are you that smoking will make your child's illness worse?". Higher scores indicate higher perceived vulnerability.⁷⁷⁻⁷⁹

6. Benefits of quitting. We will assess whether the caregiver perceives that quitting smoking would have a beneficial effect on their child using the adapted precaution-effectiveness measures by Borelli, et. al. Precaution Effectiveness-Child (PE-C) will be measured by items including: "If you stop smoking, how much would that decrease your child's symptoms?". Higher scores indicate higher perceived vulnerability.⁷⁷⁻⁷⁹

7. Child's SHSe. Child's SHSe will be assessed by asking about family and other individuals with whom the child came in contact during the past week who smoke, locations of smoking, and number of cigarettes smoked. We will use questions adapted from previous studies.^{52,80-83} Caregivers who report no smoking indoors, outdoors, or in a car will be considered to have a complete smoking ban. Epic chart review will be conducted to assess SHSe-related PED visits and hospitalizations to CCHMC for 6-months prior to baseline.

8. Healthy Lifestyle Habits. We will assess healthy lifestyle practices (daily fruit/vegetable/sugary drink consumption, daily exercise and screen time) of all children.

9. Consumer satisfaction measure. SBIRT and HHC caregivers will complete a satisfaction survey measuring intervention satisfaction and perceived usefulness.⁸⁴

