We will use GLMM to evaluate the relative effectiveness of the SBIRT versus HHC group on our primary outcomes: point prevalence and prolonged abstinence at 6-months. The analysis will be repeated with caregiver level differences between groups included as covariates. We will use mixed model analysis of covariance, with repeated measures to assess change (controlling for baseline differences between groups) to assess the effect of the SBIRT on secondary outcomes including reduction in use, number of quit attempts, and changes in readiness to quit. Kappa statistic will be used to assess agreement between the caregiver's self-report and the assessment of tobacco use based on expired carbon monoxide levels and/or salivary cotinine at 6 months. It is possible that use of and adherence to the NRT will influence outcomes in the intervention group. In addition, some of the participants in the control condition may obtain NRT during the study interval. We will examine NRT use or dose, defined as self-reported adherence, as a covariate in order to control for this possible relationship.

Analyses for Primary Aims 1-3.

Primary Aim 1, Hypothesis 1: We hypothesize that SBIRT participants will have higher prolonged abstinence and point prevalence cessation rates compared to those in the HHC group. As stated above, our primary approach to the analysis is using multiple imputation, with clinical counselors/intake coordinators/research coordinators included in the model. We shall then use analysis of covariance, to control for any baseline differences of caregivers between conditions. In addition we will also control for motivation to quit, considered a priori as a potential covariate, using the score on the contemplation ladder. As we are stratifying on motivation to quit and caregiver gender, we will initially enter this into the model as an interaction. To address child cotinine as the 6-month outcome, we will use a t-test and then an analysis of covariance to incorporate the variables different at baseline. Incorporating the 6-week outcome values, we will use GLMM invoking GEE for the repeated

measures and also a model including covariates. This approach will be used to assess the intervention's effect on abstinence and point prevalence and child cotinine.

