In the final analysis, the entire theoretical model to predict outcome will be examined using structural equation modeling (SEM). The strength of SEM in examining the entire model is that this method allows for the analysis of a hypothesized pattern of directional and non-directional linear relationships among a set of latent variables (e.g., caregiver beliefs about their child's SHSe risk) and measured variables (e.g., point prevalence).¹⁰³ This approach will allow us to examine the effect of perceived risk of SHSe and perceived child benefits of quitting; we will incorporate the former as latent variables over the study period. We will also be able to examine the relative relationship of caregiver's beliefs and readiness to quit with the outcome of cessation.

Analyses for Secondary Aim 1. Working closely with [name] (health services and economic consultant), we will collect the cost data needed to conduct a cost analysis of the SBIRT intervention. The cost inventory may include costs and charges from the baseline PED visit and hospitalization (if the child is hospitalized) and from SHSe-related PED visits or hospitalizations for the period 6 months before and 6 months after the baseline visit. The cost inventory will also include data collected from CRCs and clinical counselors/intake coordinators/research coordinators in both conditions about cessation-related activities and expenses, self-reported abstinence, and use of all tobacco products at each follow-up. Cost inputs will include staff time for tobacco screening, chart flagging, cessation counseling, giving informational materials and NRT, and referral to the QL, smokefreeTXT, or smokefree.gov. To determine costs of SHSe-related PED visits and hospitalizations

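### The Aim 3 mediation models are logistic because the mediators are called mainly categorical, yet most are measured as scores; a two-way split would lose about a third or more of the indirect effect

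*Combined protocol and SAP*

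**What the plan says.** Under Primary Aim 3, Hypothesis 3, the mediation analysis uses a system of logistic regressions with a Monte Carlo step to obtain direct, indirect and relative indirect effects. The ground given is: "Three sets of logistic regression analyses will be performed, as the variables of interest; outcome, intervention and mediator are mainly categorical". On the sequence it says: "The first 2 steps are to assess the intervention effects on the outcome and the mediator". The third step relates each mediator to abstinence.

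The list of mediators begins: "The mediating variables that will be considered are: perception of child's risk from SHSe and the benefits to the child of quitting". Motivation to quit and self-efficacy complete it.

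The measures are described elsewhere:

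- **Risk perception and benefits of quitting** (Baseline Assessment, items 3 and 6). Both entries end with: "Higher scores indicate higher perceived vulnerability". The number of items, response points and scoring rule are not given.
- **Motivation** (Baseline Assessment, item 1). The plan collects "motivation to quit using the Contemplation Ladder, and stage of change in readiness to quit". In the Aim 1 analysis motivation enters the model "using the score on the contemplation ladder".
- **Stage of change** (Randomization). Ordered categories are used as a stratification factor.
- **Self-efficacy.** No measure appears in Table 1 or in the list of measures.

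The structural equation model (SEM) that closes Aim 3 covers perceived risk and perceived child benefit. It says "we will incorporate the former as latent variables over the study period" and assumes linear relationships.

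**The concern.** The model is chosen because of what kind of variable the mediator is said to be, and the plan's own measurement section disagrees. A logistic model with the mediator as outcome cannot take a multi-point score unless the score is first put into categories.

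A grouped mediator carries only part of the score's information. The share of the intervention effect that runs through the discarded part is not captured as indirect effect, so it appears as direct effect. The relative indirect effect is therefore biased low as well as imprecise. That quantity is what Aim 3 is meant to report: how much of the SBIRT effect passes through risk perception and motivation.

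Quitters are also few. At the planned rates, 300 per group gives about 300 × 0.063 + 300 × 0.12 = 55 on point prevalence and 300 × 0.021 + 300 × 0.07 = 27 on prolonged abstinence.

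**Working it through.** **What can be reproduced.** The documents give no power, path size or cut-point for mediation, so there is no stated figure to match.

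**Inputs from the documents (Sample Size and Power Estimates).** 300 per group after 20% loss, or 375 under multiple imputation; point prevalence 6.3% vs 12%; prolonged abstinence 2.1% vs 7%.

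**Assumed, because not stated.** Normal mediator score; SBIRT shift d of 0.2 to 0.5 SD (0.2 to 0.3 for power); odds ratio for abstinence of 1.5 to 2.0 per SD; two-sided 0.05; a mediated path counted as shown when both component paths are significant.

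**1. Closed form.** Let b be the effect of the score on the outcome per SD, and let the score be cut at c with a fraction q below. A small shift d moves about d·φ(c) of caregivers across the cut. The two groups differ in mean score by φ(c)/[q(1−q)]. The product is d·b·φ(c)²/[q(1−q)], against d·b uncut, so the share kept is φ(c)²/[q(1−q)].

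- Median: 0.3989²/0.25 = 0.637, loss 36%.
- 67/33: loss 41%. 75/25: 46%. 80/20: 51%. 90/10: 66%.
- Equal-sized ordered groups kept as groups: loss 21% (three), 14% (four), 10% (five).

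**2. Logistic models at the planned rates, large sample, probability scale.**

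| Two-way cut at percentile | Indirect effect lost |
|---|---|
| 20th | 55–61% |
| 50th | 35–37% |
| 67th | 33–37% |
| 75th | 35–41% |
| 80th | 38–45% |

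Because abstinence is uncommon, a moderate cut above the median does no worse than the median here, while a low cut does much worse. About a third remains close to the minimum.

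**3. What this does to the reported share.** Take 6.3% vs 12% (total effect 5.7 points), d = 0.3 and OR 2.0 per SD. The true indirect effect is 1.94 points, and 1.94/5.7 = 34%. A median split loses 36% of it: 1.94 × 0.64 = 1.24 points, and 1.24/5.7 = 22%. The missing 0.70 points are reported as direct effect.

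**4. Power, 300 per group, 800 simulated trials per cell: score kept vs median split.**

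| d, OR per SD | 6.3% vs 12% | 2.1% vs 7% |
|---|---|---|
| 0.2, 1.5 | 53% vs 27% | 33% vs 15% |
| 0.3, 1.5 | 77% vs 46% | 51% vs 25% |
| 0.25, 1.75 | 83% vs 53% | 68% vs 35% |
| 0.3, 2.0 | 95% vs 80% | 87% vs 58% |

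The drop is about 15 to 33 points. At 375 per group it is 7 to 28 points. A five-level ordered score costs only about 1 to 9 points. Simulation error is at most √(0.25/800) = 1.8 points per cell.

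**The case against.** A reader might infer that the plan will dichotomise every mediator, and that the mediated share is therefore understated as written. The documents do not support that.

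- **No cut is stated.** The wording is hedged (mainly categorical). The planned look at intervention effects by mediator level implies grouping, but for a separate subgroup analysis.
- **Only the second step forces grouping.** Where abstinence is the outcome, a logistic model accepts an uncut score as predictor. An ordinal logistic model in the second step would keep the levels at modest cost.
- **One mediator has a truly categorical form.** Stage of change is collected, and the hypothesis refers to readiness to quit.
- **Response formats are unknown.** The questionnaires are listed only as appendix titles, so a near-normal score is an assumption.
- **The SEM needs no cut.** It offers a second view of the risk-perception pathway.
- **Aim 3 is framed as exploratory.** The conclusions of Aims 1 and 2 are unaffected.

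A reader might also take one third as a ceiling on the loss. It is nearer the floor for a two-way split, and too high if three or more levels are kept.

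All of this limits the claim, but the mismatch stands. Stage of change does not cover risk perception or benefits of quitting, and motivation is tied to the ladder. No ordinal model is named. The SEM does not correct the direct, indirect and relative indirect effects from the logistic system, and no rule says which result prevails if the two disagree.

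**Conclusion.** The concern holds in conditional form. The stated reason for an all-logistic system conflicts with the plan's own description of three of the four named mediators, and its second step cannot be run on those scores without a grouping that the plan does not define.

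If a roughly normal score is split in two, the loss of indirect effect is about 36% at the median. For uneven splits it reaches 40 to 60% or more, although at the planned rates a moderate cut above the median stays near a third. The lost part moves into the direct effect. Power for the mediated path falls by roughly 15 to 33 points at 300 per group. With three to five ordered levels the loss of indirect effect is 10 to 21%.

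The percentages rest on normality. The power figures also rest on assumed path sizes (d 0.2 to 0.3, OR 1.5 to 2.0 per SD) and a two-sided 0.05 level. The plan should be changed on this point, because leaving the coding open also leaves the choice of cut until after the data are seen.

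**What to change.** In the mediation paragraph of Primary Aim 3:

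- State how each mediator is coded, and keep every score-type mediator as its score.
- For the second step, fit a linear model for the mediator (ordinal if there are few response levels) with arm and the baseline score.
- For abstinence, fit a logistic model with arm and the mediator score.
- Report direct and indirect effects with Monte Carlo or bootstrap intervals.
- Use a binary logistic mediator model only where the mediator is truly binary. If stage of change is used for readiness, say so and keep its ordered levels.

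The cost is SAP rewording and a standard mediation routine in place of the all-logistic system. No new data are needed.
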